**11.6. Appendix 6: Derived and Transformed Data**

**11.6.1. General**

No investigational study drug is being administered during this study. No data are transformed.

**Date of Enrollment**

An Evaluable Subject is a subject that was not a screen failure and also met the IPSS and/or BPE/BPO entry criteria (IPSS  $\geq 8$  and/or BPE/BPO  $\geq 3$ ). The Date of Enrollment is the later of the Screening date and IPSS and BPE/BPO assessment completion dates.

Study Day is calculated as the number of days from the Date of Enrollment:

- Enrollment Date = Missing → Study Day = Missing
- Reference Date < Enrollment Date → Study Day = Reference Date – Enrollment Date
- Reference Date  $\geq$  Enrollment Date → Study Day = Reference Date – (Enrollment Date) + 1

**11.6.2. Study Population**

**Demographics**

**Age**

Only year of birth is collected in the eCRF. For purposes of calculating age for a given subject, date of birth will be defined as June 30th of the corresponding year of birth. Age is calculated in terms of Screening (Visit 1) date and output as a truncated integer. Age categories include <65,  $\geq 65$ , <75,  $\geq 75$  years.

Race				
Race will be determined based on a subject's reported geographic ancestry as defined in the following table. Race information will not be presented for subjects who were enrolled in the study in France.				
Race				
	Asian	White	Other	
Geographic Ancestry	Any combination of (restricted to the categories below only): -Asian – East Asian Heritage -Asian – Japanese Heritage -Asian – South East Asian Heritage -Asian – Central / South Asian Heritage	Any combination of (restricted to the below categories only) -White – Arabic/North African Heritage -White – White/Caucasian/European Heritage	African American/African Heritage American Indian or Alaskan Native Native Hawaiian or Other Pacific Islander	
Diagnostic Tests and Questionnaires				
IPSS (total score)				
IPSS (total score) = Sum of IPSS individual questions 1-7.				
BPE/BPO (total score)				
BPE/BPO (total score) = Sum of BPE/BPO individual questions 1-3.				

**11.7. Appendix 7: Premature Withdrawals & Handling of Missing Data**

**11.7.1. Premature Withdrawals**

Element	Reporting Detail
General	
 
• Subject study completion (i.e. as specified in the protocol) was defined as completing Visits 1, 2, and 3.
 
• Withdrawn subjects were not replaced in the study.
 
• All available data from subjects who were withdrawn from the study will be listed and all available planned data will be included in summary tables and figures, unless otherwise specified.
 
• Number and percent of Evaluable subjects completing the study and those withdrawing from the study, along with eCRF recorded reasons for premature withdrawals, will be summarized.
 

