#### **5.5. Subject and Study Completion**

A completed subject is one who has completed all study visits.

The end of the study is defined as the last subject’s last visit.

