## 6.1. Time and Events Table

| Procedure   | VISIT 1:
Screening/
Enrolment at GP Clinic | Study Period
(1 week $\pm$ 4 days to 6 weeks) |   |
|---|--|--|---|
|   |  | VISIT 2 (phone call):
GP                      | VISIT 3: Urologist 
(up to 6 weeks after V1) |
| Informed consent  | X  |  |   |
| Inclusion and exclusion criteria  | X  |  |   |
| Demography  | X  |  |   |
| Medical history   | X  |  |   |
| Concomitant medications (all ongoing and within 30 days prior to Visit 1)       | X  |  |   |
| IPSS screening tool   | X  |  |   |
| BPE/BPO screening tool  | X  |  |   |
| PROCEDURES AFTER SUBJECT IS ENROLLED:                        |  |  |   |
| Urine strip test    | X  |  |   |
| Urinalysis (only if urine strip test is positive)                   | X  |  |   |
| PSA blood test    | X  |  |   |
| Results phone call to subject                                       |  | X  |   |
| Digital rectal exam (DRE)   | X  |  | X   |
| Brief physical examination  |  |  | X   |
| Enter prostate-related results in the CRF from non-protocol required procedures |  |  | X   |
| AE/SAE review (related to study procedures and/or participation)                |  | ←=====→  |   |
| Concomitant medication review   |  | ←=====→  |   |

1. Subject is enrolled after meeting eligibility requirements, which includes a positive BPE/BPO screening tool and/or positive IPSS screening tool.
2. Urinalysis sent to local laboratory only if urine strip test is positive.
3. PSA blood test sent to local lab. Local lab results and reference ranges are entered in the CRF.
4. For Visit 2, the GP calls the subject to report yes or no for probable BPH. If the subject has probable BPH, the GP schedules the subject for Visit 3 with the urologist. If the subject does not have probable BPH, then the subject has completed the study.
5. DRE is performed by the urologist. The GP may conduct a DRE at visit 1 however the DRE will be repeated by the urologist to confirm the diagnosis and to rule out an abnormality suggesting prostate cancer..
6. Information collected during visit 3 will be entered into the eCRF by the Principal Investigator.

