### 6.3. Subject Disposition

A subject may withdraw from the study at any time at the investigator's discretion or at the request of the subject.

The reason for study withdrawal is recorded in the eCRF for Evaluable subjects who prematurely withdrew from the study prior to completing Visits 1, 2, and 3. A tabular summary will be produced for number and percentage of subjects prematurely withdrawing from the study, overall and by reason. Additional tabular summaries will be produced by Visit (overall and by reason) for subjects withdrawing from the study. For these summaries, the percentages are calculated using the number of subjects in each of the categories (IPSS $\geq$ 8, BPE/BPO $\geq$ 3, IPSS $\geq$ 8 and BPE/BPO $\geq$ 3, and IPSS $\geq$ 8 or BPE/BPO $\geq$ 3) as the denominators.

Listings will be produced for subject disposition and reason for withdrawal and will include key accountability data including study status, completion or withdrawal date, all visit dates, and the primary reason for premature withdrawal.

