**11.7.2. Handling of Missing Data**

Element	Reporting Detail
General	
 
• No investigational study drug is being administered during this study.
 
• Subjects are not randomized or dispensed study treatment. As designed in the protocol, the number of subjects will decrease from the screening period to GP Assessment (Part I) and then again in the subsequent Urologist Assessment (Part II) either due to not qualifying for progression to the next part of the study or due to any withdrawal.
 
• The decreases, along with planned multiple summary and analysis types, will impact and restrict the evaluable population for a given endpoint. Therefore, populations are not defined in the traditional sense. There are no ITT or Per Protocol populations in this study. The analysis population will be All Evaluable Subjects.
 
• Missing data occurs when any requested data is not provided, leading to blank fields on the collection instrument :                         
 
○ These data will be indicated by the use of a “blank” in subject listing displays. Unless all data for a specific visit are missing in which case the data is excluded from the table.
 
○ Answers such as “Not applicable” and “Not evaluable” or “Not Done” are not considered to be missing data and should be displayed as such.
 
○ Due to the design of the study and types of endpoints incorporated, ‘observed cases’ will be summarized. For the primary analyses, there will be no imputations for missing data, no imputations for missing responses within the BPE/BPO or IPSS screening tools, and no imputations for subjects withdrawing from the study or not qualifying for a subsequent part of the study.
 
 
 

Outliers	
 
• Any subjects excluded from the summaries and/or statistical analyses will be documented along with the reason for exclusion in the clinical study report.
 

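### The SAP's completion rule requires all three visits, which contradicts the rule that a man without probable BPH finishes the study at Visit 2

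*SAP*

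**What the plan says.** Two rules for completing the study stand in the current documents.

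- **Finished at Visit 2.** Footnote 4 of the Time and Events Table (Protocol 6.1) covers the man whom the GP telephones to say he has no probable BPH: "If the subject does not have probable BPH, then the subject has completed the study". The protocol synopsis (Overall Design) and Protocol section 2 say the same, and SAP Appendix 2 carries the footnote over.
- **Finished only after Visit 3.** SAP 11.7.1 says completion "was defined as completing Visits 1, 2, and 3", makes no exception, and presents this as the protocol's definition. Protocol 5.5 is more general: "A completed subject is one who has completed all study visits". It does not say whether Visit 3 counts as a study visit for a man who is never referred.

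On reporting, SAP 11.7.1 plans to summarise "Number and percent of Evaluable subjects completing the study and those withdrawing from the study", together with the withdrawal reasons recorded in the eCRF. SAP 6.3 says a reason is recorded for Evaluable men "who prematurely withdrew from the study prior to completing Visits 1, 2, and 3". For the withdrawal tables, "the percentages are calculated using the number of subjects in each of the categories", meaning the screening-tool categories. SAP 3.2 also allows only two end states before the final analysis: completed or withdrawn.

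**The concern.** A man whom the GP judges not to have probable BPH cannot attend Visit 3, because the design ends his participation at the Visit 2 telephone call. A rule that requires three visits therefore classes a planned exit as a failure to complete. This is systematic: it applies to every man on that route.

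What is at stake is the disposition reporting: Table 1.11 (disposition), Tables 1.12 and 1.13 (discontinuation by visit, and reasons by period) and the related listings. A programmer who follows SAP 11.7.1 would understate completion. If the remaining men are then counted as withdrawals, planned exits are mixed with real losses. Those tables could also disagree with Tables 2.49 to 2.54 in the same report, which count losses stage by stage.

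**Working it through.** **Comparing the rules.** Take a man who completes Visit 1, is told at Visit 2 that he has no probable BPH, and goes no further.

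- Footnote 4, in both documents: he has completed.
- SAP 11.7.1: he has not completed, since Visit 3 is missing.
- Protocol 5.5: undecided.
- Protocol 5.4: he does not obviously fit as a withdrawal, since he has not asked to leave, has not been withdrawn for safety, behavioural or administrative reasons, and is not lost to follow-up.
- SAP 11.7.2: the fall in numbers is attributed to two distinct causes, "either due to not qualifying for progression to the next part of the study or due to any withdrawal". He belongs to the first. That distinction is not carried into the completion definition or the two-class summary.

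The SAP thus conflicts with the protocol and with its own Appendix 2. SAP 2.1 declares no change from the protocol's planned analysis, so nothing suggests that a new definition was intended.

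**Size.** The contradiction rests on no figure. The only planning number that bears on its size is the yield in Protocol 8.2: 33% of 1,500 screened men. It reproduces: 0.33 × 1,500 = 495, which the plan rounds to about 500.

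The documents do not give E, the number of Evaluable men. I assume that 500 men are referred and all attend Visit 3, that every other Evaluable man is told at Visit 2 that he has no probable BPH, and that E lies between 35% and 80% of 1,500. The share that finished as the protocol intends but fails SAP 11.7.1 is then

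(E − 500) / E

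| Share of 1,500 | E | Finished at Visit 2 | Share failing SAP 11.7.1 |
|---|---|---|---|
| 35% | 525 | 25 | 25/525 = 4.8% |
| 40% | 600 | 100 | 100/600 = 16.7% |
| 50% | 750 | 250 | 250/750 = 33.3% |
| 60% | 900 | 400 | 400/900 = 44.4% |
| 80% | 1,200 | 700 | 700/1,200 = 58.3% |

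Under the footnote 4 rule, completion is 100% in every row.

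**With some real loss.** Suppose 10% of the 500 referred men (50) miss Visit 3, leaving 450.

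- SAP 11.7.1, non-completion (E − 450)/E: 150/600 = 25.0% and 450/900 = 50.0%.
- Footnote 4 rule, non-completion 50/E: 50/600 = 8.3% and 50/900 = 5.6%.

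So in this example the same 50 lost men appear inside a non-completion figure of 25.0% to 50.0%, against 5.6% to 8.3% under the protocol's rule.

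**The case against.** The strongest reply is that the conflict is one of wording and that the output may still be right. Three parts of it stand.

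- **Withdrawal status comes from the eCRF.** SAP 6.3 describes men who "prematurely withdrew from the study prior to completing Visits 1, 2, and 3"; it does not say that every man without Visit 3 withdrew. If sites record men without probable BPH as completed, they will not appear as withdrawals. A reader might infer that all these men will certainly be reported as premature withdrawals, but the documents do not support that. What follows from the text is that they fail the completion definition; being listed as withdrawn is possible, not certain. Even in the favourable case, the tables would be right only by departing from SAP 11.7.1.
- **The important loss is already reported.** A reader might infer that men with probable BPH who never reach the urologist would be hidden. They would not be. Tables 2.49 to 2.51 cover loss before the GP assessment. Tables 2.52 to 2.54 cover loss before the urologist visit among the men eligible for it. The accountability summary (SAP 6.2, Table 1.6) counts men with a GP 'Yes', and those among them with a urologist assessment, so the gap can be read directly.
- **The primary result is untouched.** Its denominator requires a urologist assessment (SAP 7.1.2), so neither the proportion nor its interval depends on the completion flag.

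It is also fair to say that the ambiguity starts in Protocol 5.5. That explains the SAP wording but does not remove the conflict with footnote 4.

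**Conclusion.** The contradiction is real and can be seen from the documents alone. SAP 11.7.1 is wrong as written: applied literally, it gives a wrong completion count for every man whose participation properly ends at Visit 2. Whether these men are also listed as withdrawals depends on eCRF status, which the documents do not settle.

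The size cannot be fixed, because E is not stated. With 500 men referred and all attending, the misclassified share is 4.8% to 58.3% for 525 to 1,200 Evaluable men, and 16.7% to 44.4% for 600 to 900. These are illustrations of an assumption, and no narrower range can be defended from the plan. The consequence is confined to disposition reporting, so the severity is minor.

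**What to change.** In SAP 11.7.1, SAP 6.3 and Protocol 5.5, adopt one definition that agrees with footnote 4:

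- a man the GP judges not to have probable BPH completes the study with Visits 1 and 2;
- a man with probable BPH completes it with Visits 1, 2 and 3.

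In the disposition table, show 'completed at Visit 2, no probable BPH' as its own row, separate from completion at Visit 3 and from withdrawal. Tables 2.49 to 2.54 need no change.

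The cost is a few sentences and one derived flag. The GP's yes/no assessment is already used in the planned accountability table, so no new data are needed. I see no downside.

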**11.7.2. Handling of Missing Data**

Element	Reporting Detail
General	
 
• No investigational study drug is being administered during this study.
 
• Subjects are not randomized or dispensed study treatment. As designed in the protocol, the number of subjects will decrease from the screening period to GP Assessment (Part I) and then again in the subsequent Urologist Assessment (Part II) either due to not qualifying for progression to the next part of the study or due to any withdrawal.
 
• The decreases, along with planned multiple summary and analysis types, will impact and restrict the evaluable population for a given endpoint. Therefore, populations are not defined in the traditional sense. There are no ITT or Per Protocol populations in this study. The analysis population will be All Evaluable Subjects.
 
• Missing data occurs when any requested data is not provided, leading to blank fields on the collection instrument :                         
 
○ These data will be indicated by the use of a “blank” in subject listing displays. Unless all data for a specific visit are missing in which case the data is excluded from the table.
 
○ Answers such as “Not applicable” and “Not evaluable” or “Not Done” are not considered to be missing data and should be displayed as such.
 
○ Due to the design of the study and types of endpoints incorporated, ‘observed cases’ will be summarized. For the primary analyses, there will be no imputations for missing data, no imputations for missing responses within the BPE/BPO or IPSS screening tools, and no imputations for subjects withdrawing from the study or not qualifying for a subsequent part of the study.
 
 
 

Outliers	
 
• Any subjects excluded from the summaries and/or statistical analyses will be documented along with the reason for exclusion in the clinical study report.
 

**11.7.2.1. Handling of Missing Dates**

Element	Reporting Detail
General	Partial dates will be displayed as captured in subject listing displays.
Adverse Events	
 
• The eCRF allows for the possibility of partial dates (i.e., only month and year) to be recorded for AE start and end dates; that is, the day of the month may be missing. In such a case, the following conventions will be applied for calculating the time to onset and the duration of the event: 
 
○ Missing Start Day: First of the month will be used unless this is before the start date of the study; in this case the study start date will be used.
 
○ Missing Stop Day: Last day of the month will be used, unless this is after the stop date of the study; in this case the study stop date will be used.
 
 
 
• Completely missing start or end dates will remain missing, with no imputation applied. Consequently, time to onset and duration of such events will be missing.
 
• Start or end dates which are completely missing (i.e. no year specified) will remain missing, with no imputation applied.
 

**11.7.2.2. Handling of Partial Dates**

Element	Reporting Detail
General	Partial dates will be displayed as captured in subject listing displays.
Concomitant Medications	
 
• Partial dates for any concomitant medications recorded in the CRF will be imputed using the following convention: 
 
○ If the partial date is a start date, a '01' will be used for the day and 'Jan' will be used for the month
 
○ If the partial date is a stop date, a '28/29/30/31' will be used for the day (dependent on the month and year) and 'Dec' will be used for the month.
 
 
 
• The recorded partial date will be displayed in listings.
 

Adverse Events	
 
• Any partial dates for adverse events will be raised to data management. If the full date cannot be ascertained, the following assumptions will be made: 
 
○ If the partial date is a start date, a '01' will be used for the day and 'Jan' will be used for the month.
 
○ However, if this results in a date prior to Week 1 Day 1 and the event could possibly have occurred while on study from the partial information, then the Week 1 Day 1 date will be assumed to be the start date.
 
○ The AE will then be considered to start on-study (worst case).
 
○ If the partial date is a stop date, a '28/29/30/31' will be used for the day (dependent on the month and year) and 'Dec' will be used for the month.
 
 
 
• The recorded partial date will be displayed in listings.
 

## 11.8. Appendix 8: Adverse Event Time Periods and Special Adverse Event Definitions

Date-related derivations and transformations related to adverse events (AEs) are described below.

AE Onset Time since Enrollment

= AE Onset Date – Enrollment Date if Enrollment start date > AE onset date

= AE Onset Date – Enrollment Start Date +1 if Enrollment start date <= AE start date

= missing otherwise

AE Duration (in days) = AE Resolution Date – AE Onset Date + 1

If the AE onset date is partially missing, the timing is determined as follows:

1. If the non-missing parts of the date (either just year or year/month) are unambiguously before the start of enrollment, the AE is considered Pre-Enrollment.
2. If the non-missing parts of the date are unambiguously after Visit 3, the AE is considered post-study.
3. If #1 or #2 above cannot be assigned, then the AE is considered during the study.

For computing AE duration, partial AE start and end dates will be imputed as previously described, and events with completely unknown (missing) end dates will be censored at the latter of the following two dates: date of last clinic visit, latest AE start date. AE duration is the total number of non-overlapping days for all events per subject, and will be considered censored if any contributing event is censored.

Time to death is defined as (date of death – enrollment date +1). For subjects who do not experience death, time to death is censored at the date of last clinic visit (if missing, the subject will be censored at the enrollment start date).

Special interest adverse events, including MedDRA preferred terms (MedDRA Version 19.1) and codes, are presented below in Tables A-D:

[Table A](#): Sexual and Breast Adverse Events of Special Interest

[Table B](#): Prostate Cancer Adverse Events of Special Interest

[Table C](#): Cardiovascular Adverse Events of Special Interest

[Table D](#): Infrequent Tier 1 Adverse Events of Special Interest

Table A Sexual and Breast Adverse Events of Special Interest: MedDRA Preferred Terms and Codes		
Special Interest Event	MedDRA Preferred Term	PT_Code
Altered (Decreased) Libido	Sexual dysfunction	10040477
	Male sexual dysfunction	10057672
	Libido decreased	10024419
	Loss of libido	10024870
	Libido disorder	10061221
Impotence	Erectile dysfunction	10061461
	Organic erectile dysfunction	10052004
	Disturbance in sexual arousal	10058929
	Psychogenic erectile dysfunction	10052005
Ejaculation Disorders	Ejaculation delayed	10014325
	Ejaculation disorder	10014326
	Ejaculation failure	10014328
	Retrograde ejaculation	10038967
	Anorgasmia	10002652
	Orgasm abnormal	10031085
	Premature ejaculation	10036596
	Male orgasmic disorder	10025513
	Orgasmic sensation decreased	10052449
	Semen volume decreased	10039944
Breast Disorders	Breast hyperplasia	10006256
	Breast enlargement	10006242
	Gynaecomastia	10018800
	Nipple disorder	10029417
	Breast engorgement	10006240
	Breast swelling	10006312
	Breast pain	10006298
	Breast tenderness	10006313
	Nipple pain	10029421
	Nipple swelling	10058680
	Breast discomfort	10049872
Breast Disorders: Breast Enlargement	Breast hyperplasia	10006256
	Breast enlargement	10006242
	Gynaecomastia	10018800
	Nipple disorder	10029417
	Breast engorgement	10006240
	Breast swelling	10006312
Breast Disorders: Breast Tenderness	Breast pain	10006298
	Breast tenderness	10006313
	Nipple pain	10029421
	Nipple swelling	10058680
	Breast discomfort	10049872

Table B. Prostate Cancer Adverse Events of Special Interest: MedDRA Preferred Terms and Codes		
Special Interest Event	MedDRA Preferred Term	PT_Code
Prostate Cancer	Prostate cancer	10060862
	Prostate cancer stage 0	10036912
	Prostate cancer stage I	10036917
	Prostate cancer stage II	10036918
	Prostate cancer stage III	10036919
	Prostate cancer stage IV	10036920
	Prostate cancer recurrent	10036911
	Prostate cancer metastatic	10036909

Table C. Cardiovascular Adverse Events of Special Interest: MedDRA Preferred Terms and Codes		
Special Interest Event	MedDRA Preferred Term	PT_Code
Acute Coronary Syndrome	Acute myocardial infarction	10000891
	Myocardial infarction	10028596
	Silent myocardial infarction	10049768
	Sudden cardiac death	10049418
	Angina unstable	10002388
	Cardiac arrest	10007515
	Cardio-respiratory arrest	10007617
	Cardiac death	10049993
Ischemic Cerebrovascular Events	Acute coronary syndrome	10051592
	Cerebrovascular accident	10008190
	Transient ischemic attack	10044390
	Cerebral infarction	10008118
	Cerebrovascular disorder	10008196
	Cerebral artery embolism	10008088
	Cerebral artery occlusion	10008089
	Cerebral artery thrombosis	10008092
	Ischemic stroke	10061256
	Cerebral circulatory failure	10008097
	Cerebellar infarction	10008034
	Thalamic infarction	10064961
	Reversible ischemic neurologic deficit	10050496
	Thrombotic stroke	10043647
	Embolic stroke	10014498
	Vertebral artery occlusion	10048965
	Carotid arterial embolus	10007684
	Carotid artery occlusion	10048964
	Carotid artery stenosis	10007687
	Carotid artery thrombosis	10007688
	Thrombotic cerebral infarction	10067347
	Brain stem infarction	10006147
	Embolic cerebral infarction	10060839
	Lacunar infarction	10051078
Brain stem stroke	10068644	
Stroke in evolution	10059613	
Ischaemic cerebral infarction	10060840	

Table C Cardiovascular Adverse Events of Special Interest: MedDRA Preferred Terms and Codes (continued)		
Special Interest Event	MedDRA Preferred Term	PT_Code
Cardiac Failure	Cardiac failure congestive	10007559
	Cardiac failure	10007554
	Left ventricular failure	10024119
	Cardiac failure acute	10007556
	Cardiogenic shock	10007625
	Left ventricular failure acute	10063081
	Right ventricular failure	10039163
	Right ventricular failure acute	10063082
	Ventricular failure	10060953
	Cardiopulmonary failure	10051093
Ischemic Coronary Artery Disorders/ Atherosclerosis	Congestive cardiomyopathy	10056370
	Coronary artery embolism	10011084
	Coronary artery occlusion	10011086
	Coronary artery stenosis	10011089
	Coronary artery thrombosis	10011091
	Myocardial ischemia	10028600
	Coronary artery disease	10011078
Cardiac Arrhythmias	Arteriosclerosis coronary artery	10003211
	Ventricular extrasystoles	10047289
	Torsade de Pointes	10044066
	Ventricular fibrillation	10047290
	Cardiac Fibrillation	10061592
	Pulseless electrical activity	10058151
	Ventricular asystole	10047284
	Long QT syndrome	10024803
	Ventricular tachycardia	10047302
Ventricular Arrhythmia	10047281	
Peripheral Vascular Disease	Ventricular flutter	10047294
	Deep Vein Thrombosis	10051055

Table D. Infrequent Tier 1 Adverse Events of Special Interest: MedDRA Preferred Terms and Codes		
Special Interest Event	MedDRA Preferred Term	PT_Code
Relevant for dutasteride:		
Allergic reactions	Anaphylactic reaction	10002198
	Anaphylactic shock	10002199
	Anaphylactic transfusion reaction	10067113
	Anaphylactoid reaction	10002216
	Anaphylactoid shock	10063119
	Circulatory collapse	10009192
	Kounis syndrome	10069167
	Shock	10040560
	Type I hypersensitivity	10045240
	Allergic oedema	10060934
	Angioedema	10002424
	Circumoral oedema	10052250
	Conjunctival oedema	10010726
	Corneal oedema	10011033
	Epiglottic oedema	10015029
	Eye oedema	10052139
	Eye swelling	10015967
	Eyelid oedema	10015993
	Face oedema	10016029
	Gingival oedema	10049305
	Gingival swelling	10018291
	Gleich's syndrome	10066837
	Hereditary angioedema	10019860
	Idiopathic angioedema	10073257
	Idiopathic urticaria	10021247
	Laryngeal oedema	10023845
	Laryngotracheal oedema	10023893
	Limbal swelling	10070492
	Lip oedema	10024558
	Lip swelling	10024570
	Mouth Swelling	10075203
	Oculorespiratory syndrome	10067317
	Oedema mouth	10030110
	Oropharyngeal swelling	10031118
	Palatal oedema	10056998
	Palatal swelling	10074403
	Periorbital oedema	10034545
	Pharyngeal oedema	10034829
	Scleral oedema	10057431
	Swelling face	10042682
	Swollen tongue	10042727
	Tongue oedema	10043967
	Tracheal oedema	10044296
Urticaria	10046735	
Urticaria cholinergic	10046740	
Urticaria chronic	10052568	
Urticaria papular	10046750	
Acquired epidermolysis bullosa	10056508	
Blister	10005191	
Blister rupture	10073385	
Bullous impetigo	10006563	

Table D. Infrequent Tier 1 Adverse Events of Special Interest: MedDRA Preferred Terms and Codes		
	Conjunctivitis	10010741
	Corneal exfoliation	10064489
	Drug eruption	10013687
	Epidermolysis	10053177
	Epidermolysis bullosa	10014989
	Genital ulceration	10018180
	HLA-B*1502 assay positive	10074771
	HLA-B*5801 assay positive	10074774
	Lip exfoliation	10064482
	Mouth ulceration	10028034
	Mucocutaneous ulceration	10028084
	Mucosa vesicle	10028103
	Mucosal erosion	10061297
	Mucosal exfoliation	10064486
	Mucosal necrosis	10067993
	Mucosal ulceration	10028124
	Nikolsky's sign	10029415
	Noninfective conjunctivitis	10074701
	Oral mucosal blistering	10030995
	Oral mucosal exfoliation	10064487
	Oral papule	10031010
	Oropharyngeal blistering	10067950
	Pemphigoid	10034277
	Pemphigus	10034280
	Penile exfoliation	10064485
	Skin erosion	10040840
	Skin exfoliation	10040844
	Staphylococcal scalded skin syndrome	10041929
	Stomatitis	10042128
	Tongue exfoliation	10064488
	Vaginal exfoliation	10064483
	Vaginal ulceration	10046943
	Vulval ulceration	10047768
	Vulvovaginal rash	10071588
	Vulvovaginal ulceration	10050181
	Application site pruritus	10003053
	Aquagenic pruritus	10003071
	Injection site pruritus	10022093
	Pruritus	10037087
	Pruritus genital	10037093
	Rash pruritic	10037884
	Senile pruritus	10039986
	Itching scar	10050818
	Eyelids pruritus	10051627
	Catheter site pruritus	10052270
	Pruritus generalised	10052576
	Infusion site pruritus	10053664
	Vulvovaginal pruritus	10056530
	Incision site pruritus	10059386
	Uraemic pruritus	10060875
	Pruritus allergic	10063438
	Instillation site pruritus	10063763
	Implant site pruritus	10063785

Table D. Infrequent Tier 1 Adverse Events of Special Interest: MedDRA Preferred Terms and Codes			
	Cholestatic pruritus	10064190	
	Polymorphic eruption of pregnancy	10066100	
	Vessel puncture site pruritus	10067254	
	Vaccination site pruritus	10068881	
	Brachioradial pruritus	10071443	
	Notalgia paraesthetica	10072643	
Breast Cancer	Apocrine breast carcinoma	10066206	
	Invasive breast carcinoma	10075713	
	Triple negative breast cancer	10075566	
	Breast cancer	10006187	
	Breast cancer female	10057654	
	Breast cancer in situ	10006189	
	Breast cancer male	10061020	
	Breast cancer metastatic	10055113	
	Breast cancer recurrent	10006198	
	Breast cancer stage I	10006199	
	Breast cancer stage II	10006200	
	Breast cancer stage III	10006201	
	Breast cancer stage IV	10006202	
	Breast sarcoma	10068582	
	Breast sarcoma metastatic	10068583	
	Breast sarcoma recurrent	10068584	
	Electron radiation therapy to breast	10014437	
	Extended radical mastectomy	10015721	
	Gamma radiation therapy to breast	10017677	
	HER-2 positive breast cancer	10065430	
	Inflammatory carcinoma of breast recurrent	10021977	
	Inflammatory carcinoma of breast stage III	10021978	
	Inflammatory carcinoma of breast stage IV	10021979	
	Inflammatory carcinoma of the breast	10021980	
	Intraductal papillary breast neoplasm	10073540	
	Intraductal proliferative breast lesion	10073094	
	Invasive ductal breast carcinoma	10073095	
	Invasive lobular breast carcinoma	10073096	
	Invasive papillary breast carcinoma	10073098	
	Lobular breast carcinoma in situ	10073099	
		Malignant nipple neoplasm	10062051
		Malignant nipple neoplasm female	10053129
	Malignant nipple neoplasm male	10053128	
	Mastectomy	10026878	
	Medullary carcinoma of breast	10027095	
	Metaplastic breast carcinoma	10073100	
	Modified radical mastectomy	10027799	
	Mucinous breast carcinoma	10073101	
	Neuroendocrine breast tumour	10073103	
	Oestrogen receptor assay positive	10054054	
	Oestrogen receptor positive breast cancer	10070577	
	Paget's disease of nipple	10033364	

Table D. Infrequent Tier 1 Adverse Events of Special Interest: MedDRA Preferred Terms and Codes		
	Photon radiation therapy to breast	10034949
	Postmastectomy lymphoedema syndrome	10036390
	Progesterone receptor assay positive	10054057
	Radical mastectomy	10037773
	Radiotherapy to breast	10062090
	Simple mastectomy	10040700
	Tubular breast carcinoma	10073104
	X-ray therapy to breast	10048199
	Antioestrogen therapy	10002816
	Breast reconstruction	10006305
	Breast neoplasm	10006279
	Nipple neoplasm	10056286
	Phyllodes tumour	10071776
	Biopsy breast abnormal	10004745
	Breast calcifications	10048782
	Breast dysplasia	10006237
	Breast prosthesis implantation	10006303
	Computerised tomogram breast abnormal	10074534
Depressed mood	Activation syndrome	10066817
	Adjustment disorder with depressed mood	10001297
	Columbia suicide severity rating scale abnormal	10075616
	Adjustment disorder with mixed anxiety and depressed mood	10001299
	Agitated depression	10001496
	Anhedonia	10002511
	Antidepressant therapy	10054976
	Childhood depression	10068631
	Decreased interest	10011971
	Depressed mood	10012374
	Depression	10012378
	Depression postoperative	10012390
	Depressive symptom	10054089
	Dysphoria	10013954
	Electroconvulsive therapy	10014404
	Feeling guilty	10049708
	Feeling of despair	10016344
	Feelings of worthlessness	10016374
	Major depression	10057840
	Menopausal depression	10067371
	Post stroke depression	10070606
	Postictal depression	10071324
	Completed suicide	10010144
	Depression suicidal	10012397
	Intentional overdose	10022523
	Intentional self-injury	10022524
	Poisoning deliberate	10036000
	Self-injurious ideation	10051154
	Suicidal behaviour	10065604

Table D. Infrequent Tier 1 Adverse Events of Special Interest: MedDRA Preferred Terms and Codes		
	Suicidal ideation	10042458
	Suicide attempt	10042464
Hair changes	Alopecia	10001760
	Alopecia areata	10001761
	Alopecia scarring	10001764
	Alopecia syphilitic	10001765
	Alopecia totalis	10001766
	Alopecia universalis	10001767
	Hypotrichosis	10021126
	Progeria	10036794
	Madarosis	10051235
	Follicular mucinosis	10056506
	Application site alopecia	10059046
	Androgenetic alopecia	10068168
	Satoyoshi syndrome	10070579
	Radiation alopecia	10072045
	Diffuse alopecia	10073736
Hypertrichosis	10020864	
Interference with formation of external genitalia in a male fetus	Congenital vas deferens absence	10010670
	Cryptorchism	10011498
	Epispadias	10015088
	Hypospadias	10021093
	Reproductive tract hypoplasia, male	10057858
	Testicular dysplasia	10059271
	Congenital genital malformation male	10059492
	Penoscrotal fusion	10064951
	Sertoli-cell-only syndrome	10066833
	Buried penis syndrome	10067131
	Penoscrotal transposition	10067287
Penile torsion	10070235	
Potential for decreased male fertility	Infertility tests	10021931
	pH semen	10034784
	pH semen decreased	10034786
	pH semen increased	10034788
	pH semen normal	10034790
	Red blood cells semen	10038176
	Red blood cells semen negative	10038179
	Red blood cells semen positive	10038180
	Semen liquefaction	10039931
	Semen liquefaction normal	10039933
	Semen liquefaction prolonged	10039934
	Semen liquefaction shortened	10039935
	Semen viscosity	10039936
	Semen viscosity decreased	10039938
	Semen viscosity increased	10039940
	Semen viscosity normal	10039942
	Semen volume abnormal	10039943
	Semen volume decreased	10039944
	Semen volume increased	10039946
	Semen volume normal	10039948
Sperm analysis	10041476	
Sperm analysis abnormal	10041477	
Sperm analysis normal	10041478	

Table D. Infrequent Tier 1 Adverse Events of Special Interest: MedDRA Preferred Terms and Codes		
	Spermatozoa abnormal	10041498
	Spermatozoa morphology	10041501
	Spermatozoa morphology abnormal	10041502
	Spermatozoa morphology normal	10041503
	Spermatozoa progressive motility abnormal	10041504
	Spermatozoa progressive motility decreased	10041506
	Spermatozoa progressive motility normal	10041507
	White blood cells semen	10047956
	White blood cells semen negative	10047959
	White blood cells semen positive	10047960
	Fructose semen decreased	10052476
	Fructose semen increased	10052477
	Prostatic fluid leukocytes increased	10053866
	Infertility tests abnormal	10062020
	Infertility tests normal	10062021
	pH semen abnormal	10062074
	Semen liquefaction abnormal	10062159
	Semen viscosity abnormal	10062160
	Semen analysis normal	10062238
	Semen analysis	10068482
	Semen analysis abnormal	10068483
	Sperm concentration decreased	10070925
	Sperm concentration increased	10070926
	Sperm concentration abnormal	10070927
	Sperm concentration normal	10070928
	Sperm concentration	10070929
	Sperm concentration zero	10070930
	Total sperm count	10070931
	Total sperm count decreased	10070932
	Infertility	10021926
	Infertility male	10021929
Testicular pain and swelling	Anorchism	10002641
	Eunuchoidism	10015532
	Hypogonadism male	10021011
	Testicular atrophy	10043298
	Testicular disorder	10043306
	Testicular failure	10043315
	Testicular failure postoperative	10043317
	Testicular failure primary	10043318
	Testicular hyperfunction	10043334
	Testicular infarction	10043337
	Testicular pain	10043345
	Testicular retraction	10043348
	Testicular swelling	10043354
	Testicular torsion	10043356
	Testicular necrosis	10049572
	Spermatic cord mass	10049792
	Testicular appendage torsion	10050476
	Spermatic cord pain	10051221

Table D. Infrequent Tier 1 Adverse Events of Special Interest: MedDRA Preferred Terms and Codes		
	Testicular injury	10051872
	Testicular haemorrhage	10051877
	Epididymal calculus	10052321
	Epididymal enlargement	10052322
	Epididymal tenderness	10052323
	Testis discomfort	10052531
	Monorchidism	10055002
	Epididymal disorder	10055045
	Spermatic cord disorder	10056348
	Testicular mass	10058901
	Testotoxicosis	10063654
	Spermatic cord haemorrhage	10065742
	Spermatic cord obstruction	10065805
	Spermatic cord perforation	10065806
	Spermatic cord stenosis	10065807
	Testicular perforation	10065808
	Testicular hypertrophy	10066101
	Testicular oedema	10066769
	Sperm granuloma	10067802
	Testicular microlithiasis	10067829
	Congenital monorchidism	10069505
	Testicular autoimmunity	10071574
Relevant for tamsulosin:		
Atrial fibrillation, tachycardia, arrhythmias	Arrhythmia	10003119
	Heart alternation	10058155
	Heart rate irregular	10019304
	Pacemaker generated arrhythmia	10053486
	Pacemaker syndrome	10051994
	Paroxysmal arrhythmia	10050106
	Pulseless electrical activity	10058151
	Reperfusion arrhythmia	10058156
	Withdrawal arrhythmia	10047997
	Arrhythmia supraventricular	10003130
	Atrial fibrillation	10003658
	Atrial flutter	10003662
	Atrial parasystole	10071666
	Atrial tachycardia	10003668
	Junctional ectopic tachycardia	10074640
	Sinus tachycardia	10040752
	Supraventricular extrasystoles	10042602
	Supraventricular tachyarrhythmia	10065342
	Supraventricular tachycardia	10042604
	ECG P wave inverted	10057526
	Electrocardiogram P wave abnormal	10050384
	Retrograde p-waves	10071187
	Anomalous atrioventricular excitation	10002611
	Cardiac flutter	10052840
	Extrasystoles	10015856
	Tachyarrhythmia	10049447
	Accelerated idioventricular rhythm	10049003
	Cardiac fibrillation	10061592
Parasystole	10033929	
Rhythm idioventricular	10039111	

Table D. Infrequent Tier 1 Adverse Events of Special Interest: MedDRA Preferred Terms and Codes		
	Torsade de pointes	10044066
	Ventricular arrhythmia	10047281
	Ventricular extrasystoles	10047289
	Ventricular fibrillation	10047290
	Ventricular flutter	10047294
	Ventricular parasystole	10058184
	Ventricular pre-excitation	10049761
	Ventricular tachyarrhythmia	10065341
	Ventricular tachycardia	10047302
Floppy Iris Syndrome	Floppy iris syndrome	10066373
Orthostasis	Dizziness	10013573
	Dizziness postural	10013578
	Orthostatic hypotension	10031127
	Hypotension	10021097
	Syncope	10042772
	Presyncope	10036653
